3: PK blood samples, in the intervention arm only, will be taken once during the intensive phase of TB treatment at either Week 4 **OR** Month 2 (**PK bloods may be repeated at Month 2 if these were not taken, incorrectly done or incomplete at Week 4 OR at the discretion of the investigator**), and at the end of TB treatment (Month 6)

4: Additional PK samples will be taken at M7 (or the first visit after if Month 7 is missed) in Intervention Arm before and after the ingestion of the single additional dose of Moxifloxacin. This additional PK sample may be deferred to month after TB treatment completion on participants who have TB treatment extended beyond 6 months

5: If PBMCs are not collected at baseline samples may be taken at Week 4 or Month 2

6. End of TB Treatment visit will be conducted within 7 days of completion of TB treatment.

\* Samples will be collected and stored for future susceptibility testing,

\*\*ECG's will be done at baseline, Month 2 and Month 4 and Month 6. ECG's will be performed 2 monthly during treatment with Moxifloxacin

\*\*\*Additional PBMC's will be collected at IRIS and at the time of seroconversion

The study SoE will be followed except when procedures are clinically indicated as not required.

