## 8.0 CLINICAL MANAGEMENT ISSUES

### 8.1 Clinical Management Issues

The IMPRESS study will use the Division of AIDS Table for Grading the Severity of Adult and Paediatric Adverse Events (DAIDS AE Grading Table) Version 1.0, December 2004 (Clarification, August 2009)

- Patients need to be assessed for evidence of musculoskeletal toxicity at every study visit through history taking and physical examination.
- Ocular toxicity will be assessed using the Snellen and Ishihara tests at baseline and month 2 and/or when clinically required (Control Arm only). Patients will be educated about symptoms of ocular toxicity before treatment initiation, and will be assessed for ocular toxicity for the duration of TB therapy when Ethambutol forms part of the TB regimen. The Snellen and Ishihara tests will be repeated if any symptoms of ocular toxicity or any change in vision occurs.

- All patients will undergo ECG monitoring at baseline, Month 2, Month 4, Month 6 (and 2 monthly whilst being administered with Moxifloxacin). This will be repeated if patients complain of chest pain or syncope. Moxifloxacin will be substituted for Ethambutol if there is evidence of QT prolongation, or if patients QRS complexes change in amplitude from baseline.
- Patients must not have evidence of severe or life-threatening liver disease at baseline (Bilirubin, AST and ALT < 5 times the ULN), no evidence of renal impairment i.e. creatinine clearance of > 60 mls/min, serum potassium of > 3.0 mmol/l.

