### QTc Prolongation

Participants in this trial may receive Moxifloxacin which has the potential to prolong the QTc interval. All QTc measurements will be corrected with the Fridericia correction.

The protocol-specific criteria for grading prolonged QTc are as follows:

PARAMETER	GRADE 1 MILD	GRADE 2 MODERATE	GRADE 3 SEVERE	GRADE 4 POTENTIALLY LIFE- THREATENING
Prolonged QTc (using Fridericia QT correction formula)	Asymptomatic, QTc interval 0.45 – 0.47 sec	Asymptomatic, QTc interval > 0.47- < 0.50 sec	Asymptomatic, QTc interval $\geq$ 0.50 sec OR a QTc > 0.48 sec with an increase in interval $\geq$ 0.06 sec above baseline	Life threatening consequence, eg, Torsade de pointes or other associated serious ventricular dysrhythmia

If Grade 2 QTc prolongation develops during the course of the study and is felt to be due to study medications, the participant will be monitored more closely, with twice weekly visits and QTc evaluation. If Grade 3 QTc prolongation occurs, all study drugs will be discontinued and the participant will be referred to hospital for further assessment and management. If the QTc prolongation is considered most likely to be due to concomitant illness or medication, standard management, including discontinuation of the likely causative agent, should be undertaken.

If a participant develops Grade 4 QTc prolongation, he or she will be hospitalized and discontinued from study medications. If the prolongation is felt to be caused by a concomitant medication and resolves with discontinuation of that agent, study medications may be restarted. Otherwise, the participant will be referred to the NTP for treatment of his or her TB according to local standards of care. The participant will continue to be followed on study, off study drugs.

Serious adverse events will be reported to the MCC and the UKZN Biomedical Research Ethics Committee. (BREC) according to their specific requirements.

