### 3. INTERIM DATA ANALYSIS AND DATA MONITORING

The CAPRISA SOP on DSMB preparations (SOP # CA STA 06) will be used to ensure that the quality of the data being used for this report is of high and reliable quality.

Interim results will include a summary of screening and enrolment, a summary of status for all enrolled participants (completed, discontinued early, possibly lost to follow-up, or continuing), retention rates, descriptive statistics of baseline variables (demographic, recent medical history), protocol violations (including both violations at enrollment/randomisation and violations after enrolment) and adverse events (including serious adverse events).

Data management quality indicators such as the total number of datafax CRF pages received, total number of QC notes placed on data received, QC rate per 100 pages, percent QC resolved, and number of days to QC resolution will be given.

For the safety data, adverse events occurring during the study will be summarised in frequency tables by study arm. Adverse events will be coded using the MedDRA system, version 15 or higher. Safety data will be summarised for all study participants who were consented, enrolled, and randomised to study arm, excluding those participants who never provided any safety data after enrollment.

No formal stopping rules are set. The Safety Monitoring Committee (SMC) should review all available safety data to determine whether there are any safety concerns and whether early termination of the study is warranted. There are circumstances in which some interpretation or flexibility may be required. If some indication of harm is found the DSMB should strongly consider taking action.

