#### **6.5. Secondary objective 2**

*To compare the proportion of patients with any Grade 3 or 4 adverse reactions*

Adverse events occurring during the study will be summarised in frequency tables by arm. The frequencies of Grade 3 and 4 adverse events will be compared between the two arms using the Fisher's exact test.

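### The SAP plans no summary of the QTcF values measured in both arms, and no QTc-specific comparison between arms at any grade

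*SAP*

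**What the plan says.** Protocol 8.1: "All patients will undergo ECG monitoring at baseline, Month 2, Month 4, Month 6". The footnote to Table 5 gives the same visits and adds that "ECG's will be performed 2 monthly during treatment with Moxifloxacin". The QTc part of Protocol 8.5 gives the reason: "Participants in this trial may receive Moxifloxacin which has the potential to prolong the QTc interval". It also fixes the method: "All QTc measurements will be corrected with the Fridericia correction". It then sets trial-specific grades:

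- Grade 1: 0.45-0.47 sec.
- Grade 2: above 0.47 and below 0.50 sec.
- Grade 3: 0.50 sec or more, or above 0.48 sec with a rise of at least 0.06 sec over baseline.
- Grade 4: life-threatening consequences.

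The SAP contains no mention of ECG or QTc. Its safety provisions are these:

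- SAP 6.5: "Adverse events occurring during the study will be summarised in frequency tables by arm". Then "The frequencies of Grade 3 and 4 adverse events will be compared between the two arms", by Fisher's exact test.
- SAP 6.6: within each arm, adverse events are compared by HIV status, with no limit on grade.
- SAP 3, for interim reports: "For the safety data, adverse events occurring during the study will be summarised in frequency tables by study arm". The Safety Monitoring Committee (SMC) "should review all available safety data to determine whether there are any safety concerns", but no QTcF table is listed for it.

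Protocol 9.2 covers culture conversion only.

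**The concern.** Moxifloxacin is given daily for about 24 weeks in place of ethambutol, and QTc prolongation is the risk for which the protocol sets its own grading scale. A measured, randomised comparison is already built into the visit schedule, yet nothing planned uses the measured values. A moderate shift in QTc would fall mostly in Grades 1 and 2, where the SAP offers only a descriptive count of whatever was recorded as an event. At Grade 3 and above, a handful of QTc events would be merged with every other severe event. The trial could end with no estimate, and no interval, for the size of the QTc effect in this population.

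**Working it through.** **The plan's own figure.** The documents give no figure for QTc; the only size calculation is for culture conversion. For 75% v 60%, two-sided 0.05 and 80% power:

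- Uncorrected n = [1.960 x sqrt(2 x 0.675 x 0.325) + 0.842 x sqrt(0.75 x 0.25 + 0.60 x 0.40)]^2 / 0.15^2 = 151.9.
- With continuity correction: (151.9 / 4) x [1 + sqrt(1 + 4 / (151.9 x 0.15))]^2 = 164.9, so 165 per arm and 330 in all.

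This matches Protocol 9.1, so 165 per arm is used below.

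**Assumed inputs.** The SD of QTcF change, the background rate of Grade 3/4 events and the QTc distribution are not in the documents. Ranges are shown for each.

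**1. What the planned Grade 3/4 test can see.** Let b be the background proportion of patients with any Grade 3/4 event and x the expected number of intervention patients with Grade 3 QTc. The intervention proportion is b + (1 - b) x/165. For b = 20% and x = 2 this is 0.20 + 0.80 x 2/165 = 21.0%. Exact rejection probabilities of Fisher's test:

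| Background | x = 0 | x = 1 | x = 2 |
|---|---|---|---|
| 10% | 3.1% | 3.4% | 4.1% |
| 20% | 3.7% | 3.8% | 4.1% |
| 30% | 3.8% | 3.9% | 4.1% |

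The test behaves almost the same with and without a QTc effect. Three extra percentage points (23% v 20%, about 5 patients) give about 8% power. A Fisher test on Grade 3 QTc alone would need at least 6 v 0 (p = 0.030; 5 v 0 gives p = 0.061).

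**2. What the measured values can show.** Half-width = t(0.975, 2n - 2) x SD x sqrt(2/n). For n = 165 and SD 20: 1.967 x 20 x sqrt(2/165) = 4.3 ms. Power is from the noncentral t distribution, two-sided 0.05.

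| SD of change | Half-width, n = 165 | Power, 10 ms | Power, 5 ms | Half-width, n = 132 (20% missing) |
|---|---|---|---|---|
| 15 ms | 3.2 ms | >99% | 86% | 3.6 ms |
| 20 ms | 4.3 ms | >99% | 62% | 4.8 ms |
| 25 ms | 5.4 ms | 95% | 44% | 6.1 ms |
| 30 ms | 6.5 ms | 86% | 33% | 7.3 ms |

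**3. Where a shift would appear.** A simulation assumed mean QTcF of 405 or 415 ms; total SD and SD of change of (20, 15), (20, 20) or (22, 25) ms; 10% of follow-up ECGs missing; and no stopping rule. With a 10 ms shift:

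- Expected Grade 3 QTc patients in the intervention arm: 0.01-0.96.
- Patients whose worst scheduled value is 450 ms or more: about 4-21 of 165 in control and 12-44 of 165 in intervention.

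Almost all of the shift lies below Grade 3. The banded counts are less sensitive than the mean. At the low end, 4 v 12 is a difference of 8/165 = 4.8 points with Fisher p = 0.070.

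**The case against.** The strongest reply is that nothing planned is wrong. QTc appears in no primary, secondary or ancillary objective, and SAP 6.5 serves its stated objective. The protocol uses the ECGs to manage individual patients: replacing moxifloxacin (8.1), and closer monitoring, stopping or referral (8.5). A value of 0.45 sec or more is a graded abnormality by the same numbers in both arms, and adverse events are tabulated by arm at all grades. If the protocol is followed, many of the banded counts should reach those tables. The SMC may also look at all safety data. This stands, and it settles the rank of the point as an improvement. It does not supply a summary of measured values or an interval.

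Three stronger readings are tempting, and the documents do not support them.

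- *QTc events below Grade 3 go unrecorded, or are recorded more fully on moxifloxacin.* The trial is open label, Protocol 8.2.5 singles out Grades 3 and 4, the QT example in 8.4 names moxifloxacin, and ECGs beyond the common visits apply only on moxifloxacin. But 8.2.5 ends by requiring that all adverse events be reported under good clinical practice guidelines. Differential recording is possible but not shown, and no recording rate can be taken from the documents.
- *No test of any kind touches events below Grade 3.* SAP 6.6 does test events of any grade, but by HIV status within arm. The accurate statement is that no QTc-specific comparison between arms exists at any grade.
- *The added analysis would settle the QTc question.* It would not. Power for 5 ms is 33-86%. Substitution and stopping would dilute Month 4, Month 6 and worst-value results as randomised, and the simulation ignores this. The protocol fixes no ECG time relative to dose, no replicates and no blinded reading, so a narrow interval could reassure too much.

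**Conclusion.** The gap is real and is an improvement worth making, not a departure from the protocol. Protocol-required QTcF measurements from both arms have no planned summary, and the only test of adverse events between arms is nearly blind to a QTc effect: 3.1-3.8% rejection with none, about 4.1% with two expected Grade 3 patients. The measured values would give a confidence half-width of 3.2-6.5 ms at 165 per arm, or 3.6-7.3 ms with 20% of ECGs missing. That is enough to show a difference near 10 ms and often too little for 5 ms. These sizes rest on assumed SDs of 15-30 ms and assumed background rates of 10-30%. The absence of any QTc analysis rests on the text alone.

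**What to change.** Add to SAP 6.5:

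- **(a)** QTcF change from baseline by arm, as randomised, at Months 2, 4 and 6, with Month 2 as the main visit. Adjust for baseline QTcF and HIV status. Report the arm difference with a 95% confidence interval.
- **(b)** Patients per arm by worst scheduled QTcF at the common visits, in the protocol's bands (0.45-0.47, above 0.47 to below 0.50, and 0.50 sec or more), and patients with a rise of 0.06 sec or more. Report the risk difference with a 95% interval suited to small counts, such as a score interval. Supply this table to the SMC.
- **(c)** A statement that Month 4, Month 6 and worst-value results may be diluted by substitution or stopping of moxifloxacin, and that ECG timing relative to dose is uncontrolled. An on-treatment version is optional.

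The cost is SAP wording, some programming and a few tables, with no new patient procedures. The documents do not show whether numeric QTcF is on the case report form. If it is not, up to 330 x 4 = 1,320 scheduled ECGs would need abstracting from source.

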#### **6.6. Secondary objective 3**

*To compare adverse events and 2-month culture conversion rates among HIV-infected patients vs. HIV-uninfected patients.*

The culture conversion rates of HIV-negative patients at the end of the intensive phase will be compared to the rates of HIV-positive patients at the end of the intensive phase using the Cochran-Mantel-Haenszel test, stratifying by study arm.

Within each study arm, the number of adverse events from HIV-negative patients will be compared to the number from HIV-positive patients using the Fisher's exact test.

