### **2.2 Secondary Objectives**

- 2.2.1 To determine the time to culture-conversion of the Moxifloxacin regimen and the Ethambutol regimen using data from 2-, 4-, 6-, and 8-week cultures
- 2.2.2 To compare the proportion of patients with any Grade 3 or 4 adverse reactions
- 2.2.3 To compare adverse events and 2-month culture conversion rates among HIV-infected patients vs. HIV-uninfected patients
- 2.2.4 To compare the rates of treatment failure and recurrence of the Intervention and Control arm.
- 2.2.5 To compare TB cure rates at month 6 and at end of TB treatment between the Intervention and Control Arm

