### 3.1 Study setting: study site and populations

The study will be conducted at the CAPRISA eThekweni Clinical Research Site (eCRS), adjoining the largest government outpatient TB facilities, the Prince Cyril Zulu Communicable Disease Centre (PCZCDC). The PCZCDC provides free diagnosis and treatment for patients with TB in Durban. The clinic is readily accessible by public transport. Over the last 3 years, TB cases in the Durban region have increased by 38%. In 2001, 7,819 received TB care, 70% had pulmonary tuberculosis. In 2008, 4179 TB patients were managed at the clinic and of these, 2204 had smear positive TB. Approximately 35% of patients have a past history of TB. The majority (91%) of TB patients are black Africans, unemployed (53%), women (39%), 69% are HIV co-infected and the median age was 33 years (range: 5-72 years). The change in number from 2001 to 2008 is due to the decentralization of TB services. In order to make treatment even more accessible and also improve case holding. Laboratory support is available onsite.

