## **9.0 STATISTICAL CONSIDERATIONS**

### **9.1 Sample size determination:**

A total of 330 patients will be enrolled. A two group continuity corrected chi square test with a 0.05 two-sided significance level will have 80% power to detect the difference between 75% of patients having culture conversion in the Intervention arm and 60% of patients having culture conversion in the Control arm. A previous unpublished retrospective review at the study site comparing the treatment outcome in retreatment

patients with TB using the standard 4 drug regimen, showed a cure and completion rate of 60.1%. According to WHO surveillance data, the retreatment regimen is successful in about 70% of patients, and other retrospective studies show treatment success rates of 26 – 92%. Thus, 75% is a realistic cure and completion rate to aim for in the Intervention group. A previous unpublished retrospective review at the study site comparing the treatment outcome in retreatment patients with TB using the standard 4 drug regimen, showed a cure and completion rate of 60.1%. According to WHO surveillance data, the retreatment regimen is successful in about 70% of patients, and other retrospective studies show treatment success rates of 26 – 92%. Thus, 75% is a realistic cure and completion rate to aim for in the Intervention group.

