### 1.2. Secondary Objectives

1. To determine the time to culture-conversion of the Moxifloxacin regimen and the Ethambutol regimen using data from 2-, 4-, 6-, and 8-week cultures
2. To compare the proportion of patients with any Grade 3 or 4 adverse reactions
3. To compare adverse events and 2-month culture conversion rates among HIV-infected patients vs. HIV-uninfected patients between the study arms
4. To compare the rates of treatment failure and recurrence of the intervention and control arm.
5. To compare TB cure rates at month 6 and at end of TB treatment between the intervention and control arm.

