## 2. STUDY DESIGN

This is an open label randomized controlled clinical trial comparing two regimens for treatment of smear-positive pulmonary TB, among patients previously treated for TB. The primary objective is to determine if a Moxifloxacin-containing regimen, substituting Moxifloxacin for Ethambutol, of 24 weeks duration is superior to a control regimen of 24 weeks duration in improving treatment outcomes in patients with recurrent TB.

This study will include adults 18 years and over with a previous history of TB. HIV infected and uninfected patients will be included in the study as well as patients on ARVs provided that these are not contra-indicated with any of the study drugs. Patients with M tuberculosis

resistance to Rifampicin will be excluded at screening using Gene Xpert technology. A maximum of 330 participants will be included in the study.

Patients will be randomized in a 1:1 ratio to receive one of the two TB retreatment regimens, as outlined in the table below.

|                         | Intensive Phase (2 months) | Continuation Phase |
|-------------------------|-----------------------------------|---------------------------|
| Intervention Arm | HRZM* daily (2 months)            | HRM* daily (4 months)     |
| Control Arm      | HRZE* daily (2 months)            | HR* daily (4 months)      |

\* Isoniazid (H), Rifampicin (R), Pyrazinamide (Z), Moxifloxacin (M), Ethambutol (E)

The duration of TB treatment may increase due to a delay in the time to sputum conversion which will result in the extension of TB treatment beyond 6 months. Following treatment, participants will be followed up on a two-monthly basis for 12 months.

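### SAP 6.6 has no combined analysis of adverse events by HIV status: it plans only a separate Fisher's exact test in each arm, so the overall HIV comparison in the objective is neither estimated nor tested

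*SAP*

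**What the plan says.** Protocol 2.2 (objective 2.2.3) states the aim as "To compare adverse events and 2-month culture conversion rates among HIV-infected patients vs. HIV-uninfected patients". The SAP 6.6 heading has the same comparison. SAP 1.2 words it differently: "To compare adverse events and 2-month culture conversion rates among HIV-infected patients vs. HIV-uninfected patients between the study arms".

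SAP 6.6 then treats the two outcomes differently:

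- Culture conversion at the end of the intensive phase is compared between HIV groups "using the Cochran-Mantel-Haenszel test, stratifying by study arm". This is one test that combines the two arm strata.
- For adverse events the rule is: "Within each study arm, the number of adverse events from HIV-negative patients will be compared to the number from HIV-positive patients". The method named is Fisher's exact test, so there are two tests, one per arm.

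SAP 5 sets a two-sided 0.05 level for every test. SAP 6.6 gives no combined adverse event estimate, no HIV-by-arm interaction or homogeneity test, no rule for reading two differing p-values, and no reason for the change of method.

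**The concern.** The objective in Protocol 2.2.3 and the SAP 6.6 heading is one comparison, HIV-infected against HIV-uninfected, for two outcomes. The plan answers it for conversion but not for adverse events. Each Fisher test uses about half of the patients, so each has much less power than a combined test. The two results are never brought together.

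The second risk is in the reading. If the HIV effect is the same in both arms, one p-value can still fall below 0.05 and the other above it. In a table laid out by arm, that invites the conclusion that one regimen is worse tolerated in HIV-infected patients, which a pair of within-arm tests cannot support.

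**Working it through.** **Inputs from the documents**

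- Total enrolment: "A total of 330 patients will be enrolled" (Protocol 9.1).
- Allocation: "Patients will be randomized in a 1:1 ratio to receive one of the two TB retreatment regimens" (SAP 2), so 165 per arm.
- HIV share: "69% are HIV co-infected" among patients at the clinic (Protocol 3.1). 0.69 × 165 = 113.85, so 114 HIV-positive and 51 HIV-negative per arm. Randomization is stratified by HIV status (Protocol 5.0), so a similar split in both arms is reasonable.
- Sensitivity value: 53% HIV co-infection among retreatment cases (Protocol 1.1), which gives 87 and 78 per arm.

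**Assumptions.** The outcome is patients with at least one event, the HIV effect is the same in both arms, and there are no losses. The documents give no adverse event rate by HIV status, so a range is shown.

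**The plan's own figure.** The only stated sizing is for the primary comparison, 75% v 60%. With mean proportion 0.675 and difference 0.15:

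- Uncorrected n per arm = [1.960 × √(2 × 0.675 × 0.325) + 0.842 × √(0.75 × 0.25 + 0.60 × 0.40)]² / 0.15² = 151.9.
- Continuity-corrected n = (151.9 / 4) × [1 + √(1 + 4 / (151.9 × 0.15))]² = 164.9, so 165 per arm and 330 in total.

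The stated 330 is reproduced. There is no corresponding figure for adverse events by HIV status.

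**Method**

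- P, the power of one within-arm Fisher test, is the summed binomial probability of all 2 × 2 tables with two-sided p ≤ 0.05 (exact enumeration).
- The arms are independent, so Pr(exactly one arm significant) = 2P(1 − P) and Pr(at least one significant) = 1 − (1 − P)².
- The CMH statistic, without continuity correction, is [Σ(a − n₁m/N)]² / Σ[n₁n₀m(N − m) / (N²(N − 1))], summed over the two arms and compared with chi-square on 1 degree of freedom. Here a is the number of HIV-positive patients with an event, n₁ and n₀ are the HIV-positive and HIV-negative numbers, m is all patients with an event and N is the arm size. Its power was found by simulation.

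**Results, 114 v 51 per arm**

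| HIV− v HIV+ rate | Each Fisher test | At least one Fisher test | CMH, both arms | Exactly one arm significant |
|---|---|---|---|---|
| 20% v 20% | 3.9% | 7.7% | 5% | 7.6% |
| 20% v 25% | 8.6% | 16% | 16% | 16% |
| 20% v 30% | 24% | 42% | 48% | 36% |
| 20% v 35% | 46% | 71% | 80% | 50% |
| 20% v 40% | 70% | 91% | 96% | 42% |
| 20% v 50% | 96% | >99% | >99% | 7.5% |
| 10% v 20% | 29% | 50% | 63% | 41% |
| 15% v 30% | 52% | 77% | 85% | 50% |
| 30% v 45% | 41% | 65% | 74% | 48% |

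**Ceiling.** 2P(1 − P) is largest at P = 0.5, where it equals 0.5. It is at least 0.40 only when P lies between about 28% and 72%.

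**Other HIV share.** At 87 v 78 per arm, the 20% v 35%, 15% v 30%, 10% v 20% and 30% v 45% cases give 39-60% power per Fisher test, 72-91% for CMH, and exactly one arm significant in 48-50%.

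**How much of the gap is due to the Fisher test itself.** At 20% v 35%, an uncorrected chi-square test in one arm has 50% power, against 46% for Fisher. So about 4 of the 34 points between Fisher and CMH come from Fisher's conservatism; the rest comes from splitting by arm.

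**The case against.** The strongest defence is SAP 1.2. Its added reference to the study arms gives a documentary reason for arm-specific results. The arms also receive different drugs (Protocol Table 1) with different listed toxicities (Protocol Table 4), so a common HIV effect is a less natural assumption for adverse events than for conversion. Both points stand as reasons to show results by arm. They do not rescue the analysis: a between-arm question needs a test of whether the HIV effect differs, and two within-arm p-values are not that test.

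A reader might infer several stronger things that the documents do not support:

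- *That identical HIV effects will split the arms in about half of trials.* Half is the ceiling, reached only for moderate effects, and no document gives rates that would favour those effects.
- *That the two arms would contradict each other.* The event calculated is significance in one arm only, not effects in opposite directions.
- *That half of the data are discarded.* Each test uses about half of the patients, but the two together use all of them.
- *That the SAP intends to claim worse tolerability of moxifloxacin in HIV-infected patients.* It states no such inference. The risk lies in how the table may be read.

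Two further reservations stand. SAP 6.6 compares the number of adverse events, whereas the figures here count patients with at least one event. They describe the written analysis only once the unit is settled that way. Also, this is a comparison by a baseline factor within a secondary objective, and no stopping rule depends on it (SAP 3 sets none).

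**Conclusion.** The concern holds in this form: as written, SAP 6.6 neither estimates nor tests the overall HIV effect on adverse events, and under the SAP 1.2 wording it does not test a between-arm difference in that effect either. This follows from the text and needs no assumption.

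The size does depend on assumptions: patients with at least one event, 165 per arm, the clinic's HIV share, an identical effect in both arms, and assumed event rates. On these, power per Fisher test against CMH is 46% v 80% at 20% v 35%, and 29% v 63% at 10% v 20%. In the moderate-effect cases, even counting a significant result in either arm has less power than CMH. It also has more false positives, 7.7% against 5% with no HIV effect and 20% affected in both groups. One-arm-only significance ranges from 7.5% to 50% across the cases shown.

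The point is worth correcting because the remedy is already in the same section. It concerns a secondary objective and leaves the primary analysis untouched.

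**What to change.** In SAP 6.6, replace the within-arm Fisher tests with the following:

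1. Define the outcome as patients with at least one adverse event and, separately, at least one Grade 3 or 4 event.
2. Compare HIV-positive with HIV-negative patients by a CMH test stratified by arm. Report a common risk ratio or risk difference with its 95% confidence interval.
3. Show the within-arm proportions with confidence intervals as description only.
4. Judge any difference between arms only by one HIV-by-arm homogeneity test.
5. Reconcile the wording of the objective in Protocol 2.2.3, SAP 1.2 and the SAP 6.6 heading.

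The cost is about one paragraph of SAP text and no new data. There is a real downside: the common estimate averages over arms that receive different drugs, and the homogeneity test is weak. With a 15-point HIV effect in one arm, none in the other and 20% of HIV-negative patients affected, a risk-difference interaction test has about 34% power at 114 v 51 per arm. The SAP should therefore say that a non-significant homogeneity test does not establish a common effect.

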## 5. GENERAL STATISTICAL ISSUES

All tests will be two-sided, and the significance level will be 0.05.

Outliers will be identified by looking at summary statistics and scatter plots. All outliers detected will be verified from the source documentation. Outliers that have biologically impossible values will be excluded from all data summaries and analyses. If one (or several) outlier(s) change(s) the interpretation of the data substantially, two summaries and analyses will be done, one with and one without the outlier(s).

If a participant has missing data at a specific time point, data at all non-missing time points for the participant will be used and included in the summaries. Missing data will be ignored (i.e. treated as missing at random) unless patterns are identified which would potentially bias analysis results.

Where applicable, analyses will be stratified by HIV status.

All statistical analyses will be done using SAS (SAS Institute Inc., Cary) version 9.4 or higher.

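### SAP 6.6 applies Fisher's exact test to numbers of adverse events, not patients, so it defines no valid 2x2 table, and its type I error can exceed 0.05 if events cluster within patients.

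*SAP*

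**What the plan says.** SAP 6.6 covers secondary objective 3. Its second paragraph states that, within each arm, "the number of adverse events from HIV-negative patients will be compared to the number from HIV-positive patients", and names Fisher's exact test as the method. The objective speaks only of comparing adverse events and names no unit. The section gives no denominator, no rule for repeated events and no count model.

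SAP 6.5 covers secondary objective 2. Its method sentence reads "The frequencies of Grade 3 and 4 adverse events will be compared between the two arms using the Fisher's exact test". The objective printed directly above it, the same as in Protocol 2.2 and SAP 1.2, is "To compare the proportion of patients with any Grade 3 or 4 adverse reactions".

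SAP 5 sets the level for all of these tests: "All tests will be two-sided, and the significance level will be 0.05". Nothing in SAP sections 3 to 5 says that a patient is counted once in an adverse-event analysis. Protocol 6.2 and 8.5 have patients asked about adverse events at each clinic visit. The protocol schema gives about 6 months of treatment plus 12 months of follow-up.

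**The concern.** Fisher's exact test conditions on the margins of a 2x2 table and treats each unit in the table as independent. The unit in 6.6 is the event, and this causes two problems.

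- **No table.** Numbers of events in two groups fill one row. The second row could hold patients without an event, visits without an event, or events of another kind. The SAP does not choose, so two analysts could report different p-values from the same data.
- **No independence.** A patient with one adverse event is plausibly more likely to have another. Counting each event as a separate unit overstates the information, and a few patients with many events could produce a spurious difference between HIV groups.

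At stake is the pre-specified p-value for the adverse-event half of secondary objective 3.

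**Working it through.** **1. The plan's own figure.** The documents give no figure for the adverse-event comparisons. The only stated calculation is for the primary endpoint: "A total of 330 patients will be enrolled", with "80% power to detect the difference between 75% of patients having culture conversion in the Intervention arm and 60% of patients" in the control arm, two-sided 0.05, continuity corrected.

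- Uncorrected n per arm = [1.960 × √(2 × 0.675 × 0.325) + 0.842 × √(0.60 × 0.40 + 0.75 × 0.25)]² / 0.15² = 151.9, so 152.
- Corrected n = (151.9/4) × [1 + √(1 + 4/(151.9 × 0.15))]² = 164.9, so 165 per arm and 330 in total.

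The figure is reproduced, and nothing below affects it.

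**2. Group sizes for 6.6.** Allocation of 330 at 1:1 (SAP 2) gives 165 per arm. Protocol 3.1 reports 69% HIV co-infection among TB patients at the clinic. Taken as an assumption for the trial, 0.69 × 165 ≈ 114 HIV-positive and 51 HIV-negative per arm.

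**3. Assumptions that the documents do not supply.** Mean events per patient 0.3 to 2. Counts are Poisson (no clustering) or negative binomial with shape 2, 1 or 0.5, where variance/mean = 1 + mean/shape. Twelve visits per patient. No true difference between the groups.

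**4. Simulation.** 3,000 runs per scenario, Fisher's exact test at two-sided 0.05. Three event-based tables were compared with the patient-level table (any event, yes or no). Entries are rejection rates for 51 v 114.

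| Mean | Shape | Events over patients | Events over visits | Share of events of one type | Patients with any event |
|---|---|---|---|---|---|
| 0.3 | Poisson | 0.086 | 0.039 | 0.029 | 0.041 |
| 0.3 | 0.5 | 0.175 | 0.115 | 0.054 | 0.047 |
| 0.5 | Poisson | 0.161 | 0.050 | 0.040 | 0.039 |
| 0.5 | 0.5 | 0.302 | 0.153 | 0.075 | 0.041 |
| 1 | Poisson | buildable in 29% of runs | 0.057 | 0.039 | 0.036 |
| 1 | 1 | buildable in 27% of runs | 0.183 | 0.107 | 0.044 |
| 2 | Poisson | never buildable | 0.065 | 0.043 | 0.035 |
| 2 | 0.5 | never buildable | 0.420 | 0.237 | 0.042 |

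Where the table cannot be built, events outnumber patients and the no-event cell would be negative. Over all 16 scenarios the patient-level test stays between 0.035 and 0.047.

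**5. Check by formula.** For a table with D denominator units per patient, the true variance of the event count exceeds the variance assumed by the test by the factor r = (1 + mean/shape)/(1 − mean/D). The rejection rate is then about 2 × [1 − Φ(1.96/√r)].

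- Mean 2, shape 0.5, D = 12: r = 5/0.833 = 6.0; 1.96/√6.0 = 0.80; rate 0.42 (simulated 0.420).
- Mean 1, shape 1, D = 12: r = 2/0.917 = 2.18; 1.96/√2.18 = 1.33; rate 0.18 (simulated 0.183).
- Mean 0.5, shape 0.5, D = 1: r = 2/0.5 = 4.0; 1.96/√4.0 = 0.98; rate 0.33 (simulated 0.302, since Fisher's test is conservative).
- Mean 0.3, Poisson, D = 12: r = 1/0.975 = 1.03; 1.96/√1.03 = 1.94; rate 0.05 (simulated 0.039).

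Group sizes do not enter the formula, so the assumed HIV split matters little. Two groups of 165 give a similar range for events over visits with clustering: 0.06 to 0.42.

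**The case against.** **The wording may be shorthand for patients with an event.** A careful statistician might build the patient-level table without being told. That reading is weaker for 6.6 than it looks. Where the SAP means participants it tends to say so, as in 6.7, and the objective behind 6.6 names no unit that would settle the matter. An obvious repair is still a repair that the SAP should state.

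**The size of the inflation is assumed.** This stands. The documents give no event rate, no dispersion and no denominator. With Poisson counts and visits as denominator the rate is 0.039 to 0.065, close to nominal, and the event-share table can also stay near 0.05. A reader might infer that the type I error of 6.6 is inflated as a matter of fact. The documents support only that it can be, depending on which table is built and how far events cluster.

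**SAP 6.5 is not the same error.** This also stands. A reader might infer from "The frequencies of Grade 3 and 4 adverse events will be compared between the two arms" that the comparison between arms is invalid too. The objective immediately above that sentence fixes the estimand as a proportion of patients, and Fisher's exact test suits that. The method sentence does not match its objective, and a patient-level reading resolves it.

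**The stakes are limited.** True: these are secondary safety comparisons, the HIV groups are not randomised, and SAP 3 sets no formal stopping rules that would use the result.

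**Conclusion.** SAP 6.6 is wrong as written: it names events as the unit for a test that needs independent units, and it supplies no second row for the table. That conclusion needs no simulation. The numerical consequence is conditional. Run on events, the test's null rejection rate lies between about 0.04 and about 0.3-0.4 across the assumed means, clustering and table constructions, against 0.035-0.047 when each patient counts once. Those figures rest on 51 v 114 patients per arm, 0.3 to 2 events per patient, 12 visits each and the stated dispersion. SAP 6.5 needs only its wording aligned with its objective. The primary analysis and N = 330 are unaffected. The change should be made because it is specific and almost free.

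**What to change.** - **SAP 6.6.** State that, within each arm, the number and percentage of patients with at least one adverse event will be compared between HIV-negative and HIV-positive patients by Fisher's exact test.
- **SAP 6.6, only if event counts are of interest.** Add that event rates per person-time will be compared with a negative binomial model or Poisson regression with robust variance. There is a case for this if events are common. At a Poisson mean of 2, 1 − e^(−2) = 86% of patients would have at least one event, and a yes/no comparison would then say little about event burden.
- **SAP 6.5.** Replace the reference to event frequencies with the proportions of patients with any Grade 3 or 4 adverse event, in line with the objective above it.

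The cost is one reworded sentence in each section, plus one optional sentence in 6.6. No new data, visits or patients are needed.
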